## The secondary objectives are:

To quantify and draw inferences on differences in:

- ankle function at 2 and 4 months
- ankle pain at 2, 4 and 6 months
- health-related quality of life (HRQoL) at 2, 4 and 6 months
- physical function at 4 and 6 months
- self-efficacy to exercise at 4 and 6 months
- exercise adherence at 2, 4 and 6 months
- risk of related complications over the initial 6 months
- cost-effectiveness of the interventions at 2 and 6 months

Outcomes	Objectives	Instruments	Timepoints
Primary	Ankle Function	Olerud and Molander Ankle Scale (OMAS)	6 months
Secondary	Ankle Function	OMAS	Baseline, 2 and 4 months
	Health-related quality of life	EQ-5D-5L	Baseline, 2, 4 and 6 months
	Pain	Pain sub-scales of the EQ-5D- 5L and OMAS	Baseline, 2, 4 and 6 months
	Physical Function	PROMIS Physical Function	Baseline, 4 and 6 months
	Self-efficacy	Self-Efficacy Exercise Score	Baseline, 4 and 6 months
	Exercise adherence	Self-reported exercise frequency	2, 4 and 6 months
	Complications	Complications Questionnaire and Case Report Form	2, 4 and 6 months
	Cost effectiveness	Health economics questionnaire	2 and 6 months

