**Self-efficacy**: assessed using the Self-Efficacy Exercise Score (23). The score measures a participant's judgment of their confidence to carry out exercise. The questionnaire has 9-items specifically about the ability to continue to exercise despite barriers. The participant scores their confidence level from 0 (not confident) to 10 (very confident), if they were to exercise 3 times per week for 20 minutes during each of the nine situations presented. The overall scores range 0 to 90, with higher scores indicating greater confidence to exercise.

**Exercise adherence**: assessed using patient reported exercise frequency.

**Complications:** fracture and treatment complications will be recorded, but particular note will be made of complications related to the interventions. (see section 10.3)

Clinical Research Protocol Template version 15.0

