## 9.4. Randomisation

Participants will be randomised by the local research team using a web-based service. Participants will be randomised at the stage they have weight bearing and movement restrictions outside of a cast or boot lifted at approximately 6 weeks (and no earlier than 4 Clinical Research Protocol Template version 15.0 CONFIDENTIAL

weeks) after injury/surgery, and eligibility has been confirmed, consent received, and baseline data completed.

The randomisation will be on a 1:1 basis to supervised versus self-directed rehabilitation, using a validated computer randomisation program managed through a secure (encrypted) web-based service by the Oxford Clinical Trials Research Unit (OCTRU). Randomisation will use a minimisation algorithm to ensure balanced allocation across the two treatment groups, stratified by centre and initial fracture management (surgical vs non-surgical). The first few participants will be randomised by simple randomisation to seed the minimisation algorithm and a probabilistic element introduced to the algorithm to ensure the unpredictability of intervention allocation.

On randomisation of a participant the central trial office, main site contact and local study team will be notified. This will take place via an automated email as part of the randomisation process.

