# 11.2. Sample Size Determination

292 (146 per arm) participants providing primary outcome data at 6 months are required to detect a difference of 8 points on the OMAS score with an estimated standard deviation of 21 with 90% power and 5% (2-sided) significance. The minimum clinically important difference for the OMAS selected in surgical trials has usually been 10 points but for this trial of physiotherapy we have chosen a smaller difference of 8 points, which is likely to be clinically important and was supported by our patient advisory group. The chosen standard deviation of 21 is based on the AIM trial (6) (SD 21.7) and the feasibility study data (SD 20.5 based on 32 participants having reached the 6 month time-point - unpublished). This equates to a standardised effect size of 0.38, a small to moderate effect. In the AFTER feasibility study there was 11% loss to follow-up (those not providing the primary outcome data). In order to allow for potential loss to follow-up of participants in the definitive trial we have inflated the sample size by 15% to 344 participants (172 per arm).

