We will also undertake a Complier Average Causal Effect (CACE) analysis which essentially compares the "compliers" in each group. Full compliance in the intervention group is defined as receiving a minimum of 4 physiotherapy sessions and partial compliance is receiving at least one physiotherapy session (i.e. starting the treatment). This will provide supporting evidence to any findings from the principal analysis. Subgroup analysis by surgical vs non-surgical treatment of the fracture, and by self-perceived self-efficacy at baseline will be undertaken using the same methodology incorporating a treatment by subgroup interaction term and presented using forest plots.

Similar methods to the primary outcome will be used to analyse continuous secondary clinical outcomes and patient reported outcomes. Complications will be reported by type for each intervention group, and, if appropriate, compared between the two groups using logistic regression models.

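### The subgroup wording points to grouping the 0–90 baseline self-efficacy score; section 11.4 should say the interaction is tested on the continuous score, with groups for display only

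*Protocol*

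**What the plan says.** Section 11.4 (its heading is run into the text under 11.3) names two moderators in one sentence: surgical versus non-surgical fracture treatment, and baseline self-efficacy. Both get the same method. For the second, the analysis "by self-perceived self-efficacy at baseline will be undertaken using the same methodology incorporating a treatment by subgroup interaction term and presented using forest plots".

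The only self-efficacy measure described is the Self-Efficacy Exercise Score in section 6.1, a sum of nine items each scored 0 to 10: "The overall scores range 0 to 90, with higher scores indicating greater confidence to exercise". The outcomes table in section 6 confirms that it is available as a moderator: "Self-Efficacy Exercise Score Baseline, 4 and 6 months".

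The protocol gives no cut-point or number of groups. It does not say that the score will be dichotomised, or that it will stay continuous. Section 11.1 leaves full analysis detail to a separate SAP, which is not at hand.

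**The concern.** A surgical/non-surgical factor comes in two groups. A 0–90 score does not, yet it is given the same subgroup term and the same display. Followed literally, the sentence leaves the SAP to decide where to cut rather than whether to cut. Grouping a near-continuous moderator discards information on how the treatment effect changes with the score, and makes the answer depend on the cut.

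The question has some practical weight. Section 5 describes lost confidence and fear of further injury as common in this age group. It also says that failing to show superiority would support withdrawing routine physiotherapy. Whether less confident patients gain more from supervision bears on that decision, and self-efficacy is one of only two moderators named. An unnecessarily weak test makes it easier to miss a real difference.

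**Working it through.** **Inputs from the protocol.** Section 11.2 gives the evaluable number: "292 (146 per arm) participants providing primary outcome data at 6 months are required". The same section sets the target at 8 OMAS points, the SD at 21, power at 90% and a two-sided alpha of 5%. Section 9.4: "The randomisation will be on a 1:1 basis to supervised versus self-directed rehabilitation".

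**The plan's own figure.** Per arm, 2 × (1.960 + 1.282)² × 21² / 8² = 144.8, so 145 by the normal approximation. The two-sample t-test version gives 145.8, so 146 per arm and 292 in all, as stated. With 15% loss, 292 / 0.85 = 343.5, so 344, as stated. The sample size is sound. The protocol states no figure for the interaction.

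**Assumptions not in the protocol.** The interaction is linear in the score, the score is roughly normal unless noted, and covariates do not reduce the variance.

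**Information kept after grouping.** This is the squared correlation between the grouped and the continuous score. For a normal score cut at quantile p it is φ(z_p)² / [p(1 − p)], which is 2/π = 0.637 at the median.

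| Grouping | Kept | Lost |
|---|---|---|
| None (continuous term) | 100% | 0% |
| Median split, normal score | 63.7% | 36.3% |
| 40/60 split, normal | 62.2% | 37.8% |
| 30/70 split, normal | 57.6% | 42.4% |
| 25/75 split, normal | 53.9% | 46.1% |
| 20/80 split, normal | 49.0% | 51.0% |
| Median split, uniform score | 75% | 25% |
| Median split, several bounded beta shapes | 65–70% | 30–35% |
| 3 equal groups, scored by group means | 79.3% | 20.7% |
| 4 equal groups, scored by group means | 86.1% | 13.9% |
| 5 equal groups, scored by group means | 89.7% | 10.3% |

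The last three rows assume a trend across ordered groups. Groups entered as an unordered factor were not computed.

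**Power, continuous term.** The standard error of the interaction per SD of self-efficacy is 2 × 21 / √292 = 2.46 OMAS points. For 80% power the slope difference must be (1.960 + 0.842) × 2.46 = 6.9 points per SD.

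**Power, median split.** The difference in treatment effect between the two halves is slope × 2 × √(2/π) = slope × 1.596. Its standard error, with four cells of 73, is 21 × √(4/73) = 4.92. For a slope of 6, the difference is 9.6 and the ratio is 9.6 / 4.92 = 1.95, against 6 / 2.46 = 2.44 for the continuous term.

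| Change in effect per SD | Continuous | Median split |
|---|---|---|
| 2 points | 13% | 10% |
| 3 points | 23% | 16% |
| 4 points | 37% | 25% |
| 6 points | 68% | 50% |
| 8 points | 90% | 74% |

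**Simulation check.** With 4,000 replicates, 292 participants, SD 21 and a slope of 6.9 points per SD, power was 79% continuous and 60% after a median split. The formula gives 80% and 61%. The split is equivalent to analysing about 292 × 0.637 = 186 participants.

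**The case against.** The strongest reply is that the protocol never commits to grouping. An interaction term can use the score as it stands, and a forest plot can show model-based effects at chosen values, so neither phrase requires categories. How a moderator is coded is also the kind of detail normally left to a SAP. This stands in part. A missing cut-point is not a fault here, and a reader should not infer that the protocol prescribes a split or that a third of the information is lost as planned. That figure needs two groups, a cut near the median, a roughly bell-shaped score and a linear interaction, and the protocol states none of these. What remains is that the form of analysis it does describe reads most naturally as grouping, and a SAP written from that sentence could inherit the weaker form.

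A reader might also infer that, in an open-label trial, the cut could be chosen to suit the results. The protocol gives little support for this. Section 11.1 has the SAP drafted early, finalised before the primary outcome analysis and reviewed by the Trial Oversight Committee, with no efficacy interim unless that committee asks for one.

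Two further points stand. The interactions for which grouping costs most power are large next to the trial's 8-point target: 6 points per SD is a 12-point change in effect between one SD below and one SD above the mean. For modest interactions the test is weak under either coding. Effect modification is also not among the listed objectives.

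**Conclusion.** The point holds as a conditional one about a supporting analysis. If the score is grouped, the loss is about 36% for a median split of a roughly normal score, and about 10% to 51% across the other groupings considered. It is zero if the unseen SAP already keeps the score continuous. At 6 points per SD, power is about 68% continuous against 50% split. These figures rest on 292 analysed, SD 21, a linear interaction, an assumed score distribution (the protocol gives none) and no variance reduction from covariates. The primary estimate, the sample size and the main conclusion are unaffected, so priority is low. It is worth raising because the better form of the test needs no extra data.

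**What to change.** In section 11.4, and to match in the SAP, state that effect modification by self-efficacy is tested with a treatment by continuous baseline score interaction in the primary model, evaluated at 6 months, with a prespecified linearity check such as a spline. Present the estimated treatment effect with its 95% confidence interval across the score. If a forest plot is wanted, show model-based effects at prespecified values, for example the quartiles, with the p-value from the continuous term. Any grouping is then for display only. The surgical/non-surgical analysis stays as written. If the SAP already does this, only the protocol sentence needs aligning.

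The cost is about one sentence in each document and slightly more analysis work, with no new data or participants. The downside is the linearity assumption: a straight-line term can miss a threshold effect that groups might show, which is why the check should be prespecified.

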## 11.5. The Level of Statistical Significance

All outcomes will be assessed with 5% level of significance and will be presented with effect sizes and 95% confidence intervals. P-values will be reported with up to 3 decimal places.

## 11.6. **Procedure for Accounting for Missing, Unused, and Spurious Data.**

Missing data will be minimised by careful data management. Missing data will be described with reasons given where available; the number and percentage of individuals in the missing category will be presented by treatment arm. All data collected on data collection forms will be used, since only essential data items will be collected. No data will be considered spurious in the analysis since all data will be checked and cleaned before analysis. The nature and mechanism for missing variables and outcomes will be investigated, and if appropriate multiple imputation will be used. However, the analysis method proposed is reasonably robust to missing at random (MAR) data. Sensitivity analyses will be undertaken to assess potential departures from the missing at random assumption. Any imputation techniques will be fully described in the Statistical Analysis Plan.

## 11.7. **Procedures for Reporting any Deviation(s) from the Original Statistical Plan**

Clinical Research Protocol Template version 15.0

CONFIDENTIAL

Any changes or deviations from the original SAP will be described and justified in the protocol, updated SAP, final report and publications as applicable, depending on the timing of the changes.

## 11.8. Health Economics Analysis

A within-trial cost-effectiveness analysis will be conducted from a NHS and Personal Social Services (PSS) perspective using the multiple imputed trial data over a period of 6 months for the base case (or primary) analysis. Trial data would consist of resource use extracted from the trial report forms and questionnaires. Unit costs for resource inputs will be drawn from a range of primary and secondary sources. Completion rates for values for each resource use and cost category will be computed by trial arm at each time-point. Utilisation of resources will be summarised by trial arm and follow-up period and differences between arms will be analysed using t-tests for continuous variables and chi-squared test for categorical variables. Means and standard errors for values of each cost category will be estimated by treatment allocation and follow-up period. Differences in mean costs will be assessed using t-tests and the bootstrap 95% confidence intervals will be computed based on 10,000 replications. The cost-effectiveness analysis will adopt an intention-to-treat ("as randomised" with imputation of missing data) approach and an incremental cost-effectiveness ratio (ICER) will be calculated as the difference in mean costs divided by the difference in mean QALYs between the trial comparators. The NICE cost-effectiveness threshold of £20,000-£30,000 per additional QALY will be used to determine the cost-effectiveness of supervised progressive exercise compared to best practice advice. Sensitivity analysis will be performed to explore the effects of (i) extending the study perspective (i.e. societal perspective where the out-of-pocket expenses and productivity loss will be included), (ii) assessing the impact of missing data (i.e. using complete case analysis) on the ICERs, and (iii) including an additional £15,000 per QALY threshold to reflect recent trends in healthcare decision-making. Findings of this economic evaluation will be reported in accordance with the Consolidated Health Economic Evaluation Reporting Standards (CHEERS) statement (https://www.ispor.org).

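### Section 11.8 names no adjustment for baseline EQ-5D utility in the QALY difference that enters the ICER, although the baseline is collected and other patient-reported outcomes are baseline-adjusted

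*Protocol*

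**What the plan says.** Protocol section 11.8 (Health Economics Analysis) plans a within-trial evaluation "using the multiple imputed trial data over a period of 6 months for the base case (or primary) analysis". It specifies the following:

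- **Costs:** "Differences in mean costs will be assessed using t-tests and the bootstrap 95% confidence intervals will be computed based on 10,000 replications".
- **ICER:** the "incremental cost-effectiveness ratio (ICER) will be calculated as the difference in mean costs divided by the difference in mean QALYs between the trial comparators".
- **Decision rule:** "The NICE cost-effectiveness threshold of £20,000-£30,000 per additional QALY will be used".
- **Sensitivity analyses:** a societal perspective, "assessing the impact of missing data (i.e. using complete case analysis) on the ICERs", and an extra £15,000 threshold.

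No covariate appears in any of these. The section gives neither a QALY formula nor an estimator or interval for the QALY difference.

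Three other places bear on the point:

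- Table 1 in section 6 lists EQ-5D-5L at "Baseline, 2, 4 and 6 months".
- Section 9.4 minimises on centre and initial fracture management only, so nothing in the design balances baseline utility.
- The statistical methods text (section 11.4, run together with 11.3) adjusts the primary OMAS model for centre, fracture management and baseline OMAS, and adds: "Similar methods to the primary outcome will be used to analyse continuous secondary clinical outcomes and patient reported outcomes".

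**The concern.** EQ-5D analysed as a patient-reported outcome would be adjusted for its baseline, whereas no adjustment is stated for the QALY built from the same questionnaire. Baseline utility enters a QALY in two ways. It is one of the points under the curve, and it is correlated with the later points. If the QALY difference is computed as a plain difference of arm means, a chance imbalance at baseline passes into the denominator of the ICER.

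What is at stake is precision and protection against chance imbalance in the economic result. Section 5 says that failure to show superiority would support disinvestment in routine physiotherapy, so the economic comparison is likely to be read closely.

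**Working it through.** The protocol gives no figure for the QALY difference, its SD or the ICER, so there is none to reproduce. The arm size does reproduce: 292/(1 - 0.15) = 343.5, rounded up to 344, or 172 per arm (section 11.2). The base case uses multiply imputed data for everyone randomised, so 172 is used below.

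**Assumptions not in the protocol:** utility SD 0.15-0.25 at every visit, correlation r = 0.3-0.7 between any two visits, and QALYs by the trapezoidal rule.

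**Step 1. Weights.** For visits at 0, 2, 4 and 6 months the weights in years are 1/12, 2/12, 2/12 and 1/12, which sum to 0.5. Baseline carries one sixth of the total.

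**Step 2. Shift from a baseline imbalance d.** The slope of QALY on baseline utility is b = (1 + 5r)/12, which is 0.208, 0.292 and 0.375 at r = 0.3, 0.5 and 0.7. The expected shift in the unadjusted difference is b × d.

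**Step 3. One-standard-error imbalance.** d = SD × √(2/172) = SD × 0.1078, which is 0.0162 at SD 0.15 and 0.0270 at SD 0.25.

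- Low end: 0.0162 × 0.208 = 0.0034 QALY, or £67 at £20,000 per QALY (£101 at £30,000).
- High end: 0.0270 × 0.375 = 0.0101 QALY, or £202 at £20,000 (£303 at £30,000).

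With 146 per arm, the number expected to give primary outcome data, the range at £20,000 is £73-£219.

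**Step 4. Precision, equal correlation between all visits.** Var(QALY) = SD² × (10 + 26r)/144. The squared correlation of QALY with baseline is ρ² = (1 + 5r)²/(10 + 26r), and adjustment multiplies the standard error by √(1 - ρ²).

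| r | ρ² | SE multiplier | SE cut | Unadjusted interval wider by |
|---|---|---|---|---|
| 0.3 | 6.25/17.8 = 0.351 | 0.81 | 19% | 24% |
| 0.5 | 12.25/23 = 0.533 | 0.68 | 32% | 46% |
| 0.7 | 20.25/28.2 = 0.718 | 0.53 | 47% | 88% |

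At SD 0.20 and r = 0.5 the standard error falls from 0.0086 to 0.0059 QALY.

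**Step 5. Precision, weaker link to baseline.** Take correlation r between baseline and each follow-up, and 0.6 between follow-ups. The ratio of adjusted to unadjusted variance is (18.6 - 25r²)/(19.6 + 10r).

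- r = 0.3: 16.35/22.6 = 0.72, SE cut 15%.
- r = 0.4: 14.6/23.6 = 0.62, SE cut 21%.
- r = 0.5: 12.35/24.6 = 0.50, SE cut 29%.

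**Step 6. Simulation check.** In 4,000 simulated trials (SD 0.20, r = 0.5, 172 per arm, no true effect) both estimators averaged close to zero (0.0002). Their SDs were 0.0087 unadjusted and 0.0059 adjusted. Correlation with the baseline imbalance was 0.73 unadjusted and 0.01 adjusted.

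**The case against.** The strongest reply is that section 11.8 is a summary. Section 11.1 leaves full details of all analyses to a separate SAP, which was not available here, and economic-model covariates are often set out there. The ICER sentence is the usual definition, and a regression-adjusted difference in mean QALYs would satisfy it.

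Much of this stands, and it rules out several stronger readings:

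- **That the plan commits to a raw QALY difference.** Section 11.8 does not say so. The t-tests are attached to resource use and costs, not to QALYs.
- **That the QALY interval is too wide.** No QALY interval is stated. The widths above describe what an unadjusted analysis would give.
- **That joint cost-QALY uncertainty will be ignored.** The only bootstrap sentence concerns costs, but joint resampling, net benefit and acceptability curves are ordinary SAP content.
- **That the result would be biased or could not support a cost-effectiveness statement.** Under randomisation the unadjusted difference is unbiased, and several thresholds and sensitivity analyses are planned.
- **That costs should also be adjusted for baseline EQ-5D.** Nothing in the protocol ties baseline utility to costs.

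The deferral does not remove the point. Section 11.8 goes into detail: it fixes the test for costs, the number of bootstrap replications, the form of the ratio and three sensitivity analyses. For costs, a t-test is an unadjusted comparison as written. A SAP that followed this text literally would leave the baseline utility unused.

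**Conclusion.** The point holds as an improvement to the analysis, not as an error or a contradiction. Section 11.8 names no baseline adjustment for the QALY difference, which is out of step with the rest of the protocol's analysis of patient-reported outcomes. If the text is followed as written, the QALY difference stays unbiased but gives up precision and remains exposed to chance imbalance.

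The sizes rest on assumed SDs and correlations. The direction is the same across every range tried: a shift of roughly three to ten thousandths of a QALY for a one-standard-error imbalance, and a standard error 15-47% smaller with adjustment across the two correlation patterns. Whether that would change the decision cannot be said, because the protocol gives neither an expected QALY difference nor a session cost. Confidence is moderate, since the SAP may already cover it.

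**What to change.** Add one or two sentences to section 11.8:

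- The incremental QALYs entering the ICER are estimated by regression within each imputed dataset, adjusted for baseline EQ-5D utility, centre and initial fracture management.
- The cost difference is adjusted for centre and initial fracture management.

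The joint bootstrap, net benefit and acceptability curves can be left to the SAP. The change is wording only. Every covariate is already collected, and neither the sample size nor trial conduct is affected. It should be settled before the SAP is finalised, so that the adjustment is fixed before the outcome data are analysed.

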## 9.5. Blinding and code-breaking

The patient-reported outcome data will be collected from participants remotely via selfreported questionnaires. It will not be possible to blind participants or those delivering the interventions.

The local research team reviewing hospital records will also not be blind to the treatment allocation.

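### The one missing-data check named for the ICER, complete-case analysis, does not test departures from MAR, and the general commitment in 11.6 is not carried over to costs and QALYs

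*Protocol*

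**What the plan says.** Section 11.8 of the protocol sets the base case of the economic evaluation as an analysis "using the multiple imputed trial data over a period of 6 months for the base case (or primary) analysis". The ICER is "calculated as the difference in mean costs divided by the difference in mean QALYs between the trial comparators"; no covariate adjustment is mentioned. The decision rule is stated as "The NICE cost-effectiveness threshold of £20,000-£30,000 per additional QALY will be used to determine the cost-effectiveness".

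The section then lists three sensitivity analyses. The first widens the perspective to societal costs. The second is "assessing the impact of missing data (i.e. using complete case analysis) on the ICERs". The third is "including an additional £15,000 per QALY threshold to reflect recent trends in healthcare decision-making". Only the second concerns missing data, and the abbreviation i.e. fixes its method rather than giving an example.

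Section 11.6, on missing data in general, says that "the analysis method proposed is reasonably robust to missing at random (MAR) data" and then promises more: "Sensitivity analyses will be undertaken to assess potential departures from the missing at random assumption". It does not mention costs, QALYs or the ICER, and 11.8 does not refer back to it.

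**The concern.** A sensitivity analysis for missing data is useful when it relaxes the assumption on which the base case depends. Here the base case depends on MAR. Complete case does not relax MAR. For an unadjusted difference in means it replaces MAR with a narrower condition and discards the partial records that imputation uses. A QALY needs EQ-5D at baseline, 2, 4 and 6 months, and costs draw on the economics questionnaire at 2 and 6 months (Table 1 in section 6), so anyone missing one of these can fall out.

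Drop-out related to recovery, and differing by arm, is plausible in this trial. Section 9.5 states: "It will not be possible to blind participants or those delivering the interventions". One arm has 4 to 6 one-to-one sessions and the other has advice materials (section 9.6). Cost-effectiveness is part of the stated aim (section 6), and section 5 says that failure to show superiority would support disinvestment in routine physiotherapy. What is at stake is an economic conclusion presented as robust on the strength of a check that could not have shown otherwise.

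**Working it through.** **Amount of missing data the plan expects.** Section 11.2 gives a difference of 8, SD 21, 90% power and two-sided 5%. The normal formula 2 × (1.960 + 1.282)² × 21² / 8² gives 145 per arm. The t-based calculation has power 0.898 at 145 and 0.900 at 146, which matches the stated 146 per arm (292). Then 292 / 0.85 = 343.5, so 344. The plan's figures reproduce, and 15% is its allowance for loss of the primary outcome. It is borrowed below for EQ-5D as an assumption.

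**What agreement or disagreement can show.** This is a large-sample simulation with assumed figures:
- 2,000,000 per arm; follow-up utility = 0.70 + 0.10x + 0.12e, with 0.024 added in the supervised arm; x is an observed baseline covariate and e is unobserved.
- True QALY difference 0.024 × 5/12 = 0.010; incremental cost fixed at £200; only utilities missing.
- Imputation is by regression on x within arm.
- MCAR: 15% missing in both arms. MAR and MNAR: about 13% missing in the self-directed arm and 14% in the supervised arm. In the supervised arm missingness depends on x (MAR) or on e (MNAR).

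| Mechanism | True ICER (£) | Complete case (£) | Imputation (£) |
|---|---|---|---|
| MCAR | 19,890 | 19,839 | 19,815 |
| MAR | 20,033 | 14,862 | 20,002 |
| MNAR | 19,850 | 14,100 | 14,091 |

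Under MAR the two methods disagree although the base case is right. Under MNAR they agree and both are wrong. Neither agreement nor disagreement identifies informative drop-out.

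**Size of a departure from MAR.** With EQ-5D at 0, 2, 4 and 6 months, the trapezoid weights in years are 1/12, 1/6, 1/6 and 1/12. If a proportion p of one arm has true utility δ below the imputed value at time points of total weight w, the QALY difference moves by p × δ × w. Take p = 0.15 and δ = 0.05 or 0.10 (assumed), and value the result at £20,000 per QALY:
- Month 6 only, w = 1/12: 0.0006 or 0.0013 QALY, about £12 or £25.
- Months 4 and 6, w = 1/4: 0.0019 or 0.0037 QALY, about £38 or £75.
- All post-baseline, w = 5/12: 0.0031 or 0.0062 QALY, about £62 or £125.

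**Effect on the ICER.** Supervised arm affected; assumed incremental cost £200; ICER = 200 / (ΔQ − pδw), with ΔQ the base QALY difference:

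| ΔQ | Base ICER (£) | Month 6 only, δ = 0.05 / 0.10 (£) | All post-baseline, δ = 0.05 / 0.10 (£) |
|---|---|---|---|
| 0.010 | 20,000 | 21,333 / 22,857 | 29,091 / 53,333 |
| 0.012 | 16,667 | 17,582 / 18,605 | 22,535 / 34,783 |
| 0.015 | 13,333 | 13,913 / 14,545 | 16,842 / 22,857 |

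In the 0.012 row, loss of month 6 alone crosses no threshold, while loss of all follow-up crosses £20,000 at δ = 0.05 and £30,000 at δ = 0.10. If both arms have the same p, δ and w, the two shifts subtract to zero.

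**The case against.** The strongest reply is that sections 11.6 and 11.8 should be read together. Section 11.6 covers missing variables and outcomes throughout the trial and already commits to examining departures from MAR. EQ-5D-5L is a listed secondary outcome, and 11.8 never says that its list is exhaustive. Details such as shift ranges belong in an analysis plan. Much of this stands. A reader might infer that the protocol makes no provision for data missing not at random; section 11.6 rules that out. What remains is that 11.6 speaks beside a statement about the proposed analysis method and does not name the ICER. Section 11.8 makes its own list and fixes the method for its missing-data item. That is a stated choice rather than detail left open.

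A second reply is that complete case is offered only to gauge the impact of missing data, not to test MAR. That is fair as to wording, but no other check on the imputed ICER is named.

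Third, a reader might infer that complete case always rests on a stronger assumption than imputation. It does not: a covariate-adjusted complete-case regression can be valid when missingness depends only on its covariates. The statement holds for the unadjusted ICER that 11.8 describes.

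Fourth, the larger figures are unfavourable cases. The 11% and 15% in section 11.2 concern OMAS at 6 months, not loss of every EQ-5D, and the shift is placed in one arm. Follow-up is run remotely with reminders, telephone and post (section 9.9). Sessions are recorded on treatment logs (section 9.8), so the main cost that differs by arm does not depend on returned questionnaires. The direction is also open, since well-recovered participants may stop responding too. All of this limits the size; it does not make complete case informative about MNAR.

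**Conclusion.** The point holds in a limited form. For the ICER as section 11.8 writes it, complete case requires roughly MCAR within arm and cannot show whether the economic conclusion survives informative drop-out. The commitment in 11.6 narrows the gap but is not tied to costs, QALYs or the ICER.

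The size is illustrative. It rests on an assumed 15% of one arm affected, utility shifts of 0.05 to 0.10 and, for the ICER figures, an assumed cost of £200 and QALY differences of 0.010 to 0.015. The range runs from about £12 per person (month 6 only) to £125 (all post-baseline EQ-5D) at £20,000 per QALY. Some scenarios cross a threshold and others do not. A reader might infer that the cost-effectiveness verdict will be reversed; the protocol gives no expected cost or QALY difference from which to say so. The point touches the secondary economic conclusion and leaves the OMAS analysis alone. It is a worthwhile, low-cost improvement.

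**What to change.** In section 11.8, keep complete case as a descriptive addition and state that the 11.6 commitment on departures from MAR applies to costs and QALYs. Name an MNAR method, for example delta-adjusted (pattern-mixture) multiple imputation; another MNAR method would also serve. Shift imputed utilities and questionnaire-based costs over a prespecified range, in either direction and separately by arm. Report the cost and QALY differences at each value, and the shift at which the ICER crosses £15,000, £20,000 and £30,000. The numerical range can sit in the statistical or health economics analysis plan.

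The tipping point is simple to report. For a utility shift in the supervised arm, with incremental cost ΔC and threshold λ, δ = (ΔQ − ΔC/λ) / (p × w). With the assumed ΔQ = 0.012, ΔC = £200, λ = £20,000 and p = 0.15, this is 0.002 / 0.0625 = 0.032 if all post-baseline EQ-5D is missing, and 0.002 / 0.0125 = 0.16 if only month 6 is. Clinicians can then judge whether such a shift is credible.

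The cost is a sentence or two in 11.8, re-use of the imputed datasets and one extra table. The downside is more scenarios to report.
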